6.5.3 Dose modifications

Dose modifications are according to investigator's discretions and follow the local product label.

6.5.4 Follow-up for toxicities

Not applicable.

6.6 Additional treatment guidance

6.6.1 Treatment compliance

The investigator must promote compliance by instructing the patient to take the study treatment exactly as prescribed and by stating that compliance is necessary for the patient's safety and the validity of the study. The patient must also be instructed to contact the investigator if he/she is unable for any reason to take the study treatment as prescribed. Compliance will be assessed by the investigator and/or study personnel at each visit using drug tablet counts and information provided by the patient or guardian via a self-administered diary card. Compliance should be ensured by the investigator to be > 80%. This information should be captured in the source document at each visit. All study treatment dispensed and returned must be recorded in the Drug Accountability Log.

6.6.2 Recommended treatment of adverse events

At present there is insufficient information to provide specific recommendations regarding treatment of AEs.

Medication used to treat AEs must be recorded on the appropriate eCRF.

6.6.3 Emergency breaking of assigned treatment code

Not applicable.

6.7 Preparation and dispensation

Each study site will be supplied with ARNI in packaging as described under investigational section. Storage must obey instructional request.

Authorized investigator and drug administrator are responsible for dispensing drug at visit 4, 5, 6 and recycling at visit 5, 6, 7. The number of ARNI distributed was calculated according to the investigator's order and the window period of treatment, and was distributed in the smallest unit, namely box. If titration adjustment is happened between two continuous visits, enough ARNI dose should take into investigator's consideration to avoid drug shorting, or investigators are responsible for reminding patient to go to site and receipt supplementary ARNI in time.

Patients must take medicine follow by doctor advice, return ARNI pack and the redundant drug. After returning back drugs at visits, authorized investigator and drug administrator are needed to check the drug tablet accord with their diary card and assess patient compliance.

In case the ARNI dosage is not enough for monthly titration modification, the investigator is obligated to remind the patients to return the site and dispense ARNI.

ACEI/ARB is prescribed by the investigators according to the clinical routine.

During the COVID-19 pandemic in which on-site study visits may be impacted, delivery of study treatment directly to a patient's home is generally permitted. If delivery is not available, patients may purchase the study drugs themselves. Patients will be reimbursed for the study drug cost with drug packaging as proof of purchase.

6.8 Handling of study treatment and additional treatment

6.8.1 Handling of study treatment

Study treatment must be received by a designated person at the study site, handled and stored safely and properly and kept in a secured location to which only the investigator and designated site personnel have access. Upon receipt, all study treatment must be stored according to the instructions specified on the labels.

Clinical supplies are to be dispensed only in accordance with the protocol. Technical complaints are to be reported to the respective Novartis Country Organization (CO) Quality Assurance.

6.8.2 Handling of additional treatment

Not applicable.

6.8.3 Instruction for prescribing and taking study treatment

The study drug dosage will be under investigator's discretion according to local guideline and product label (Table 6-2). Patients should take their morning study dose at approximately 08:00 (8 AM) and their evening study dose at approximately 19:00 (7 PM). The study medication should be taken with a glass of water with or without food. If the patient misses taking any study drug dose, he/she should take it as soon as possible, unless if it is almost time for the following scheduled dose. In this case, the patient should skip the missed dose and take the regular study drug administration schedule.

All dosages prescribed and dispensed to the patients and all dose changes during the study must be recorded in the Dosage Administration Record eCRF.

6.9 Treatment of overdose

In the event of an overdose, the Investigator should:

- Contact the medical monitor immediately.
- Evaluate the patient to determine, in consultation with the medical monitor, whether study treatment should be interrupted or whether the dose should be reduced.
- Closely monitor the participant for any AE/SAE and laboratory abnormalities for at least 30 days.
- Document the quantity of the excess dose as well as the duration of the overdose.

6.9.1 Reporting of study treatment errors including misuse/abuse

Medication errors are unintentional errors in the prescribing, dispensing, administration or monitoring of a medicine while under the control of a healthcare professional, patient or consumer (EMA definition).

Misuse refers to situations where the medicinal product is intentionally and inappropriately used not in accordance with the protocol.

Abuse corresponds to the persistent or sporadic, intentional excessive use of a medicinal product, which is accompanied by harmful physical or psychological effects.

Study treatment errors and uses outside of what is foreseen in the protocol will be recorded on the appropriate CRF irrespective of whether or not associated with an AE/SAE. Misuse or abuse will be collected and reported in the safety database irrespective of it being associated with an AE/SAE within 24 hours of Investigator's awareness. For more information on AE and SAE definition and reporting requirements, please see the respective sections.

7 Informed consent procedures

Eligible patients may only be included in the study after providing (witnessed, where required by law or regulation), Institutional Review Board/Independent Ethics Committee (IRB/IEC)-approved informed consent.

If applicable, in cases where the patient's representative(s) gives consent (if allowed according to local requirements), the patient must be informed about the study to the extent possible given

his/her understanding. If the patient is capable of doing so, he/she must indicate agreement by personally signing and dating the written informed consent document.

Informed consent must be obtained before conducting any study-specific procedures (e.g. all of the procedures described in the protocol). The process of obtaining informed consent must be documented in the patient source documents.

Novartis will provide to investigators in a separate document a proposed informed consent form that complies with the International Conference on Harmonization of Technical Requirements for Registration of Pharmaceuticals for Human Use (ICH)/ Good Clinical Practice (GCP) guidelines and regulatory requirements and is considered appropriate for this study. Any changes to the proposed consent form suggested by the investigator must be agreed by Novartis before submission to the IRB/IEC.

Information about common side effects already known about the investigational drug can be found in the label. This information will be included in the patient informed consent and should be discussed with the patient during the study as needed. Any new information regarding the safety profile of the investigational drug that is identified between label updates will be communicated as appropriate, for example, via an investigator notification (IN) or an aggregate safety finding. New information might require an update to the informed consent and then must be discussed with the patient. In the event of recollection of informed consent is needed, the Investigator may conduct the informed consent discussion remotely (e.g., telephone or video conference). Guidance issued by local regulatory bodies, and ECs/IRBs on this aspect prevail and must be implemented and appropriately documented (e.g., the presence of an impartial witness, sign/dating separate ICFs by trial participant and person obtaining informed consent, etc.).

Women of childbearing potential must be informed that taking the study treatment may involve risks to the fetus if pregnancy were to occur during the study and agree that in order to participate in the study they must adhere to the contraception requirements.

Male patients must be informed that if a female partner becomes pregnant while he is enrolled in the study, contact with the female partner will be attempted to request her consent to collect pregnancy outcome information.

8 Visit schedule and assessments

The Assessment Schedule (Table 8-1) lists all of the assessments when they are performed. All data obtained from these assessments must be supported in the patient's source documentation.

Patients should be seen for all visits/assessments as outlined in the assessment schedule (Table 8-1) or as close to the designated day/time as possible. Missed or rescheduled visits should not lead to automatic discontinuation.

Patients who discontinue from the study treatment are to complete the end of treatment visit as soon as possible, and attend the follow-up visits as indicated in Table 8-1.

Patients who discontinue from study should be scheduled for a final evaluation visit if they agree, as soon as possible, at which time all of the assessments listed for the final visit will be performed. At this final visit, all dispensed investigational product should be reconciled, and the adverse events and concomitant medications not previously reported must be recorded on

the eCRF. All treated patients should have a safety follow-up call conducted 30 days after last administration of study treatment.

Table 8-1 Assessment schedule

Period	Screening	A	CEI/ARB treatme	ent	ARNI treatment		
Visit name	1	2	3	4	5	6	7
Week/Month	0	1m (± 1w)	3m (± 2w)	6m (± 2w)	7m (± 1w)	9m (± 2w)	12m (± 2w)
Obtain informed consent	Х						
Inclusion/exclusion criteria	Х						
Demography	Х						
Date of birth							
Age							
Gender							
Race							
Height (cm)							
Weight (kg)							
BMI (kg/m²)							
Source of patient referral							
Patient HF History	Х						
Relevant medical history/current medical history	X						
Prior HF medications	Х						
Prior/Concomitant Medications	X	X	X	X	X	X	X
Implanted device	X						
Date of implantation							
ICD or CRT-D							
Primary prevention or secondary prevention							
Device data	Х	X	X	X		X	X
VA events (SVT, NSVT, PVC)							
ICD or CRT-D shocks (appropriate shocks and inappropriate shocks)							
Anti-tachycardia pacing (%)							

Physical examinations	Х	Х	Х	Х	Х	Х	Х
Electrocardiogram (ECG) data	Х		Х	Х		Х	Х
Holter monitor	Х			Х			Х
Echocardiographic data	Х			X			Х
LVEF (%)							
LVEDD (mm)							
Vital signs	X	Х	X	X	Х	X	X
Systolic blood pressure (mmHg)							
Diastolic blood pressure (mmHg)							
Heart rate average (bpm)							
Hematology test	X			X			X
Routine blood test							
Chemistry test							
Serum potassium (mEq/L)							
NT-proBNP (pg/mL)							
eGFR (mL/min/1.73m ²)							
blood pregnancy test							
Urinary pregnancy test	X			X			X
NYHA class (I-IV)	Х	Х	X	X	Х	Х	Х
Adverse Events	Х	Х	X	X	Х	Х	Х
Hospital admission data	Х	Х	X	X	Х	Х	Х
Study treatment administration	Х	Х	X	X	Х	X	Х
Study treatment dispense (ARNI)				Х	Х	Х	
Diary card collection		Х	Х	Х	Х	Х	Х
Study patient compliance assessment		Х	Х	Х	Х	Х	Х
Study completion status							Х

Abbreviations: ACEI = Angiotensin-converting enzyme inhibitor; ; ARB = Angiotensin receptor blockers; ARNI = Angiotensin receptor neprilysin inhibitor; ; CRT-D = cardiac resynchronization therapy-defibrillator;

eGFR = estimated glomerular filtration rate; ICD = Implantable Cardioverter Defibrillators;

LVEF = left ventricular ejection fraction; LVEDD = left ventricular end diastolic diameter;

NSVT = non-sustained ventricular tachycardia; NT-proBNP = N-Terminal prohormone of Brain Natriuretic Peptide;

NYHA = New York Heart Association; PVC = premature ventricular contraction; SVT = sustained ventricular tachycardia

X = assessment to be recorded in the clinical database or received electronically from a vendor; all assessments are requested to do after ICF sign, unless base on discretion from investigators, blood test and imaging report were done within 2 weeks before ICF could be acceptable.

8.1 Screening

All patients must provide informed consent before any study-specific procedure is performed. At Visit 1, patient's eligibility for entering the study will be assessed by the investigator. The date and type of implant with ICD or CRT-D will be recorded. The LVEF measurements required for eligibility will be based on obtained echocardiograms within 2 weeks before this study. Screening NT-proBNP, potassium levels, eGFR and serum creatinine and will be assessed by local hospital lab and only patients with the required values per the entry criteria will be eligible for entering the study.

8.1.1 Information to be collected on screening failures

Patients who sign an informed consent form and subsequently found to be ineligible will be considered a screen failure. The reason for screen failure should be entered on the eCRF. The demographic information, informed consent, and inclusion/exclusion pages must also be completed for screen failure patients. No other data will be entered into the clinical database for patients who are screen failures, unless the patient experienced a serious adverse event during the screening phase (see Section 10.1.3 for reporting details).

Patients who sign an informed consent and are considered eligible but fail to be started on treatment for any reason will be considered an early terminator. The reason for early termination should be captured on the appropriate disposition eCRF.

8.2 Patient demographics/other baseline characteristics

Country-specific regulations should be considered for the collection of demographic and baseline characteristics in alignment with eCRF.

Patient demographic and baseline characteristic data to be collected on all patients include: date of birth, age, gender, race, and source of patient referral. Relevant medical history/current medical history includes data until the start of study drug. Where possible, diagnoses and symptoms will be recorded. HF medications other relevant medical history will be recorded on eCRFs separately.

8.3 Efficacy assessments

8.3.1 Primary efficacy endpoint

Ventricular arrhythmia events

Cardiac arrhythmia of \geq 3 consecutive complexes originating in the ventricles at a rate >100 bpm (cycle length: <600 ms). Ventricular arrhythmia events that will be measured through device to determine SVT, NSVT and PVC:

- 1. Sustained ventricular tachycardia (SVT) is defined as tachycardia lasting for ≥30 seconds or with hemodynamic disorder as determined by Holter and/or device
- 2. Non-sustained ventricular tachycardia (NSVT) is defined as recorded by Holter and/or device

3. Premature ventricular contraction is defined as an early ventricular depolarization as determined by the device, and/or detected by Holter

The proportion of patients with VA events over 6 months of ACEI/ARB and 6 months of ARNI treatment will be measured.

Anti-tachycardia pacing and implantable cardioverter-defibrillator shocks

Once VA are detected, ICD can treat with high-energy shocks or ATP. ATP consists of one or more trains of pacing stimuli, expressed as a percentage of the tachycardia cycle length for a given RR interval, from the onset of the preceding R wave.

Patients with sustained VA events will receive ICD or CRT-D shock therapy. Inappropriate shocks may occur in patients with atrial fibrillation, SVT, or other intracardiac or extra cardiac signals. An inappropriate shock is defined as a shock not delivered for VT or VF and ending if sinus rhythm was redetected by the ICD. If a subsequent episode started within 5 minutes after the previous episode ended, it was not considered as a new episode (van Rees et al 2011).

Proportion of patients had ATP, ICD or CRT-D shocks occurrence over 6 months of ACEI/ARB and 6 months of ARNI treatment will be measured.

8.3.2 Secondary efficacy endpoints

Number of occurrences of VA

The episodes of VA events over 6 months of ACEI/ARB and 6 months of ARNI treatment will be measured.

Left ventricular ejection fraction

Left ventricular ejection fraction (%) will be compared at baseline, Month 6 and EOS.

NYHA level

NYHA level will be recorded by investigators and compared at baseline, Month 6 and EOS.

NT-proBNP

The measurements of NT-proBNP will be obtained from serum and plasma. Samples will be obtained before patients take their morning study drug dose. NT-proBNP (pg/mL) will be compared between ACEI/ARB and ARNI treatments at baseline, Month 6 and EOS.

Number of hospitalizations

Number of hospitalizations for arrhythmia or HF related hospitalizations will be recorded during ACEI/ARB and ARNI treatments.

8.3.4 Appropriateness of efficacy assessments

The efficacy assessments selected are standard for this indication/participant population.

8.4 Safety assessments

Safety assessments are specified in Table 8-2 with the assessment schedule detailing when each assessment is to be performed.

For details on AE collection and reporting, refer to AE section.

Table 8-2 Assessment & specifications

. 45.0 0 =	7.00000mont & opcomounous
Assessment	Specification
Physical examination	A complete physical examination will include the examination of general appearance, skin, neck (including thyroid), eyes, ears, nose, throat, lungs, heart, abdomen, back, lymph nodes, extremities, vascular, and neurological. If indicated based on medical history and/or symptoms, rectal, external genitalia, breast, and pelvic exams will be performed at Visit 1, Month 6 and EOS.
	Information for all physical examinations must be included in the source documentation at the study site. Clinically relevant findings that are present prior to signing informed consent must be recorded on the appropriate eCRF that captures medical history. Significant findings made after signing informed consent which meet the definition of an Adverse Event must be recorded as an adverse event.
Vital signs	Vital signs include blood pressure and heart rate measurements at every visit. After the patient has been sitting for 5 minutes, with back supported and both feet placed on the floor, systolic and diastolic blood pressure will be measured 3 times using an automated validated device, with an appropriately sized cuff. The repeat sitting measurements will be made at 1 – 2-minute intervals and the mean of the 3 measurements will be used. In case the cuff sizes available are not large enough for the patient's arm circumference, a sphygmomanometer with an appropriately sized cuff may be used.
	Clinically notable vital signs are defined in Appendix 1.
Height and weight	Height in centimeters (cm) and body weight (to the nearest 0.1 kilogram (kg) in indoor clothing, but without shoes) will be measured as specified in Table 8-1.

8.4.1 Laboratory evaluations

Hematology, chemistry tests, NT-proBNP tests, Pregnancy Test (Table 8-3) will be measured by investigators' hospital lab at baseline, Month 6 and EOS. Clinically significant abnormalities must be recorded as either medical history/current medical conditions or AEs as appropriate.

Clinically notable laboratory findings are defined in Appendix 1.

The eGFR to determine eligibility of the patient for screening will be calculated at Visit 1 from the serum creatinine concentration by using the following formula (Stevens et al 2006):

eGFR (mL/min/1.73 m²) = 175 x (standardized S_{Cr} in mg/dL)^{-1.154} x (age in years)^{-0.203} x (0.742 if female), where S_{Cr} is the standardized serum creatinine value

The eGFR will also be measured at Month 6 and EOS in order to guide the investigator to take any appropriate action as necessary. Patient will be treatment discontinuation or suspend from the study if eGFR decrease > 50% of baseline value according to investigator decision.

Table 8-3	Laboratory Assessments
Test Category	Test Name
Hematology	Red blood cells count, white blood cells count, platelet count, hemoglobin, hematocrit, and WBC differential
Chemistry	Potassium, creatinine, glucose, sodium, chloride, calcium, blood urea nitrogen, total bilirubin, fractionated bilirubin (if total bilirubin >2x ULN), aspartate aminotransferase (AST), alanine aminotransferase (ALT), alkaline phosphatase, total protein, albumin, uric acid, lipid profile, hemoglobin A1C
Kidney function	serum creatinine
Biomarkers	NT-proBNP
Pregnancy Test	Serum/Urine pregnancy test

8.4.2 Electrocardiogram (ECG)

Electrocardiograms (ECGs) must be recorded after 10 minutes rest in the supine position to ensure a stable baseline/according to the ECG investigator manual. The preferred sequence of cardiovascular data collection during study visits is ECG collection first, followed by vital signs, and blood sampling. The Fridericia QT correction formula (QTcF) should be used for clinical decisions.

A 12-lead ECG Holter recording will be performed to capture comprehensive ECG. In addition, 12-lead ECGs are collected at the study site using an ECG machine for safety assessment in real time by a qualified physician to ensure patient safety. Only clinically significant abnormalities must be reported as AE.

In the event that a clinically significant ECG abnormality is identified at the site (e.g., severe arrhythmia, conduction abnormality of QTcF > 500 ms), and the ECG is repeated to confirm the diagnosis. If the patient is hemodynamically compromised, the investigator or a medically qualified person must initiate appropriate safety procedures without delay (for example, cardioversion).

Clinically significant abnormalities must be recorded on the eCRF as either medical history/current medical conditions or AE as appropriate in related visit.

ECG data will be collected at baseline, Month 3, 6, 9 and EOS.

8.4.2.1 Cardiac imaging

LVEF (%) and left ventricular end diastolic diameter (LVEDD) (mm) will be measured by echocardiography at baseline, Month 6 and EOS.

8.4.2.2 Holter

Holter monitoring constantly records heartbeats for 24 hours and can detect arrhythmia events that might be missed by using the ECG. Data of Holter monitoring will be collected at baseline, Month 6 and EOS.

8.4.2.3 Cardiac enzymes

Not applicable.

8.4.3 Pregnancy and assessments of fertility

All pre-menopausal women who are not surgically sterile will have pregnancy testing. Additional pregnancy testing might be performed if requested by local requirements.

Pregnancy testing is required for pre-menopause women at baseline, visit 4, visit 7 of the trial. At baseline a urinary and a blood pregnancy test should be performed. If positive, the patient should be excluded. If the unpredicted pregnancy happens in the study (visit 4, 7), the patient must be discontinued from study treatment.

8.4.4 Appropriateness of safety measurements

The safety assessments selected are standard for this indication/participant population.

8.5 External central review committee

A central review committee is responsible for periodic study endpoint events adjudication and SAE review in Rhythm Study. The central review committee is an independent group consisting of individuals who have experience and expertise in the management of trial participants within heart failure area and in the monitoring of ICD/CRT-D device. The review committee will be separated to two subgroups to perform device data adjudication and SAE review respectively.

Device data report will be exported timely into PDF version by doctors at baseline, 1 month, 3 months, 6 months, 9 months, 12 months when patient visits happen in local sites and all uncertain device events will be sent to the subgroup 1 for adjudication (Device Data adjudication Boards).

All aggregated SAE data will be provided to the subgroup 2 for review (Data and Safety Monitoring Boards, DSMB).

Then committee will have a meeting held by chairman either in the site or by conference call when necessary. Central review committee members will make every attempt to attend the meeting in person or by conference call. Total central review committee members will review and interpret device data (include VA events, ICD-shock, ATP, etc) and aggregated SAE data.

The central review committee members vote on all decisions. The member must be present in the meetings or must have given written recommendation to the chair prior to the meeting. Voting is by voice vote, but any members may request a secret written ballot. After decision making, the Chairman will provide minutes of the Board discussions to all Board members provide a summary (executive) report of each Board meeting to Novartis. A summary statement and recommendation from chairman will be provided in writing to the Novartis Medical Responsible within three working days of each meeting. The recipients will acknowledge receipt and provide a response, if necessary. If an urgent report (defines according to investigator discretion) is needed to interpret, at least 3 committee members should response and give their consensus decision to the investigator.

Committee Responsibility:

1. Endpoints adjudication use for final study

- 2. Provide clinical suggestion to investigators
- 3. Make amendment for protocol to NVS, for example patient exclusion and enrollment criteria

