6.4 Treatment blinding

Treatment will be open to patients, investigator staff, persons performing the assessments, and the clinical trial team (CTT).

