12.8 Sample size calculation

12.8.1 Primary endpoint

McNemar Test is used in the primary analysis to test for 2 correlated proportions. Approximate formula from Machin et al (1997) is used to calculate the minimum size required.

For the proportion of discordant pairs, the following approximate formula is used:

Proportion Discordant =
$$P_t(1 - P_s) + P_s(1 - P_t)$$

where P_t and P_s are proportion of patients experiencing the event of interest during ACEI/ARB and ARNI treatment period respectively. Over here, both proportions are assumed to be similar to de Diego et al (2018)'s study. According to de Diego et al (2018)'s study, SVT (one of the VA event) has the following incidence 8/120 and 1/120 during ACEI/ARB and ARNI treatment period respectively. Hence, by substitute both into the equation above, proportion discordant calculated is 0.0739 after rounding off.

For the difference, a parameter under effect size is approximated by the following formula:

Effect Size =
$$P_t(1 - P_s) - P_s(1 - P_t)$$

and after substituting P_t and P_s defined above, the effect size calculated is -0.0583.

Thus, by considering the parameters defined above, power of 0.8 and significance level of 0.05, the sample size required is 175. Further consider a dropout rate of 20%, the minimum sample size required is 219.

The above calculation is calculated using PASS 11 software's Test for Two Correlated Proportion (McNemar Test) [Differences] procedure.

For proportion of patients had ICD or CRT-D shocks occurrence over 6 months of ACEI/ARB and 6 months of ARNI treatment, the above sample size will provide 95% - 98% power to detect a proportion difference of 0.075 at two-sided significance level of 0.05. The proportion difference is derived from the published literature (de Diego et al 2018).

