7.1 Overall Statistical Considerations

All statistical analyses are performed using SAS9.4.

All subjects related, efficacy related and safety related data should be collected and included in the statistical analysis. Notes or descriptive text records are only listed. For other data, descriptive statistical analysis would be performed, also statistical inference would be applied if needed.

In the statistical tabulations, screening number of subjects is the universal unique identifier of subjects in the study.

General rules of descriptive statistics: Quantitative variables are described by mean, standard deviation, standard error, median, minimum, maximum, Q1 and Q3. Categorical variables are

described by number and percentage of each category. Two-sided 95% confidence intervals will also be calculated for efficacy endpoints.

In the laboratory test part and the efficacy analysis part, 2 digits will be retained for the upper and lower limits of means and their confidence intervals, 3 digits for standard deviations, and 2 digits for medians, minimums, maximums, Q1 and Q3. In other parts, 1 digit more than the original values can be retained for the upper and lower limits of means and their confidence intervals, 2 digits more for standard deviations, and the original value digits for medians, minimums, maximums, Q1 and Q3. One decimal place will be retained for percentages and the upper and lower limits of their confidence intervals (but for efficacy analysis, 2 decimal places will be retained).

General principles of statistical inference: paired t test and Wilcoxon rank sum test will be used to compare quantitative data. McNemar test, exact test (binomial sign test) and Liddell's exact test will be used to compare categorical variables. All statistical tests will be subjected to twosided tests (unless otherwise specified), and a P-value less than or equal to 0.05 will be considered to indicate a statistically significant difference (unless otherwise specified).

For values such as "< xxx", half of the number following the less-than sign will be used to summarize and calculate statistics. For values such as "> xxx", xxx will be used to summarize and calculate statistics. For values such as "xx-xx", the average of the numbers before and after "-" will be used to summarize and calculate statistics. P value is rounded to 4 decimal places. If P < 0.0001, it is presented as '< .0001'; if P > 0.9999, it is presented as '> .9999'.

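### Protocol 8.5 specifies no masking of the endpoint adjudicators, although in this fixed-order trial the time of an event gives the drug, and it contradicts itself on who reviews device and SAE data

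*Protocol*

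**What the plan says.** - **Order of treatment.** Protocol 12.4 describes six months on ACEI/ARB followed by six months on ARNI for every patient. Protocol 5.1 requires the device to have been implanted within two weeks.
- **Blinding.** Protocol 6.4: "Treatment will be open to patients, investigator staff, persons performing the assessments, and the clinical trial team (CTT".
- **Route to adjudication.** Protocol 8.5: "Device data report will be exported timely into PDF version by doctors at baseline, 1 month, 3 months, 6 months, 9 months, 12 months". Uncertain device events are forwarded to subgroup 1. Endpoint adjudication for the final study is listed among the committee's responsibilities.
- **Who reviews what.** Section 8.5 first separates device adjudication (subgroup 1) from SAE review (subgroup 2). It then says "Total central review committee members will review and interpret device data", and the same sentence adds the aggregated SAE data.
- **Scope of subgroup 1.** Protocol section 3 has subgroup 1 confirming event types as the device defines them, without the limit to uncertain events found in 8.5.
- **SAP.** Sections 4.1.1 and 7.4.1 define and test the primary events without mentioning adjudication. Section 7.2.2 derives endpoints from CRF data.

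Neither document describes masking, redaction or shuffling of the material sent to the adjudicators.

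**The concern.** In a randomised open-label trial, a masked endpoint committee is the usual protection against classification that leans towards the expected result. Here the order is the same for everyone, so time alone gives the treatment: before Month 6 is ACEI/ARB, after it is ARNI. An adjudicator who can see the visit, the date or the time since implant can work out the drug.

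Some calls need judgement. SVT may be met through haemodynamic disorder as well as duration, NSVT is defined by the individual device, and shocks are divided into appropriate and inappropriate. The committee votes aloud unless a member asks for a secret ballot.

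Two further gaps bear on the same step. The sentence giving all members both data types undoes the separation made earlier in 8.5. And the SAP does not say which classification enters the primary tables when the site and the committee differ.

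**Working it through.** **1. The plan's own figure.** Inputs from Protocol 12.8.1: SVT "has the following incidence 8/120 and 1/120 during ACEI/ARB and ARNI treatment period respectively"; "proportion discordant calculated is 0.0739 after rounding off"; "the effect size calculated is -0.0583"; and "power of 0.8 and significance level of 0.05, the sample size required is 175". SAP 7.1 makes tests two-sided unless otherwise specified.

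- ACEI/ARB only: (8/120) × (119/120) = 0.0661
- ARNI only: (1/120) × (112/120) = 0.0078
- Sum = 0.0739; difference = 0.0583 in magnitude (the printed formula gives a plus sign; this has no bearing here)
- Exact power of the two-sided sign test, summed over Binomial(N, 0.0739): 0.7994 at N = 174 and 0.8024 at N = 175. The 175 is reproduced. The normal approximation gives 168.06, so 169.
- 175/0.80 = 218.75, so 219.

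**2. How many pairs carry the SVT result.** At N = 175:

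- 175 × 0.0661 = 11.6 pairs with SVT on ACEI/ARB only
- 175 × 0.0078 = 1.4 pairs with SVT on ARNI only
- Total 12.9. The probability that b + c reaches 25 is 0.001, so at the design rates the exact test will almost surely apply.

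**3. What one call can do.** Two-sided exact sign test, ACEI/ARB only v ARNI only:

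| Split | p |
|---|---|
| 12 v 1 (near the design expectation) | 0.0034 |
| 8 v 1 | 0.039 |
| 7 v 1 | 0.070 |

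A result near expectation is robust to single calls. A borderline one is not: changing one patient's status moves 8 v 1 to 7 v 1.

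**4. Type I error if confirmation differs by period.** Let r be the true rate in both periods (no effect), f the share of patients with an event whose status rests on an uncertain call, and u the proportion of those calls confirmed. The observed rate is r(1 − f + f·u). The two periods are taken as independent, as in the plan's own formula, and the planned rule is used (exact test if b + c < 25, otherwise chi-square) with N = 175. The documents give neither f nor u, so both are assumptions. For example, with r = 8/120, f = 0.50 and u = 0.75 v 0.25, the observed rates are 0.0583 and 0.0417.

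| Uncertain share f | r = 6.7%, 50/50 | r = 6.7%, 75/25 | r = 20% (assumed), 50/50 | r = 20% (assumed), 75/25 |
|---|---|---|---|---|
| 10% | 0.033 | 0.035 | 0.049 | 0.056 |
| 25% | 0.031 | 0.041 | 0.049 | 0.093 |
| 50% | 0.029 | 0.071 | 0.049 | 0.255 |

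The 50/50 columns show confirmation that does not depend on period, which is what masking aims at. At the SVT rate the exact test is conservative and absorbs a bias of this strength up to 25% uncertain. At a 20% rate it is exceeded from 10% uncertain. In the extreme case of 100/0 confirmation with 50% uncertain, the error at 6.7% is 0.224.

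**The case against.** The strongest reply is that most of the classification is not a matter of judgement. Protocol 12.4.1 has the events captured by the implanted device, and 11.3 requires full source verification of data for the primary variables. Only residual uncertain events reach the committee. This stands: the committee is not the only safeguard, and if few events are uncertain the bias is small.

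A reader might infer more than the documents support:

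- **That the reports are visit-labelled and the adjudicators know the drug.** Reports are exported at named visits, but the content of the forwarded packet is not described. Section 6.4 does not name the committee, 8.5 calls it independent, and no charter is among the documents. What can be said is that no masking is specified where timing would reveal the drug.
- **That aggregated SAE data reveal the drug.** Totals do not show the treatment for a given arrhythmia. The firm point is the contradiction within 8.5.
- **That three calls turn a null result into a positive one, for example 9 v 4 (p = 0.27) into 10 v 2 (p = 0.039).** The arithmetic is right but the starting split is selected. At the design rates, four or more ARNI-only pairs out of 13 has probability 0.04. With no effect at 8/120, about 22 discordant pairs are expected (175 × 2 × 0.0667 × 0.9333 = 21.8), and the same three calls move 11 v 11 to 12 v 9, p = 0.66. A call also counts only if it changes whether the patient had at least one event in the period.
- **That masking costs almost nothing.** It leaves the design figures alone, but time since implant and device counters must also be hidden, and mixing periods means holding cases back. That strains timely export, urgent reports and the committee's advice to investigators.

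**Conclusion.** The point holds as a gap in specification. Adjudication intended for the final endpoints is not masked in the text, treatment order is fixed, and 8.5 gives two incompatible accounts of who reviews device and SAE data. That contradiction needs reconciling whatever is decided on masking.

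The documents do not show that bias has occurred or will be large. Under the assumed 75/25 confirmation, type I error runs from 0.035 to 0.071 at the SVT design rate and from 0.056 to 0.255 at an assumed 20% rate, as the uncertain share goes from 10% to 50%. These figures rest on assumed uncertain shares and confirmation rates, independent periods and 175 complete pairs. The sensitivity of SVT to single calls applies to borderline splits, not to the expected one. The change is worth making because it removes a known route to bias without touching sample size, alpha or power.

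**What to change.** 1. **Protocol 8.5, masking.** Require subgroup 1 to adjudicate episodes masked to treatment period: visit, dates, drug, time since implant and cumulative device counters removed; random episode numbers; batches in mixed order. Keep urgent reports and advice to investigators on a separate, unmasked path.
2. **Protocol 8.5, division of work.** Reconcile the sentence on all members with the two-subgroup structure, so that subgroup 1 does not review SAE data by treatment.
3. **Protocol 3 and 8.5, referral.** Masking does not affect which events the unmasked sites refer. Reconcile confirmation of event types (section 3) with adjudication of uncertain events only (8.5) into one referral rule that is the same in both periods.
4. **SAP 4.1.1.** State that the adjudicated classification replaces the site's wherever one exists.

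**Cost.** Modest administrative effort for redaction and batching, which cannot be quantified from the documents, and some delay while cases from both periods are pooled. N stays at 175 evaluable and 219 enrolled. Amendment 2 records that the committee had not yet met, so at that point masking could still have covered all adjudication done at its meetings.
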